#### 11.2.5 Treatment of Adverse Events

Adverse events that occur during the study will be treated, if necessary, by established standards of care. The decision about whether the subject may continue in the study will be made by the sponsor after consultation with the investigator and/or medical monitor.

If AEs occur in a subject that are not tolerable, the investigator must decide whether to stop the subject's involvement in the study and/or treat the subject. Special procedures may be recommended for the specific IP, such as the collection of a serum sample for determining blood concentrations of IP, specific tapering procedures, or treatment regimens, as appropriate.

#### **11.2.6** Follow-up

Any AE will be followed to a satisfactory resolution, until it becomes stable, or until it can be explained by another known cause(s) (i.e., concurrent condition or medication) and clinical judgment indicates that further evaluation is not warranted. Potentially related AEs that are ongoing at the Week 8 clinic visit will be followed until they are stable, resolved, or no longer clinically significant, in the opinion of the investigator, or until 4 weeks after the study is completed. All findings relevant to the final outcome of an AE must be reported in the subject's medical record and recorded on the eCRF page.

#### 11.2.7 Notification

#### 11.2.7.1 Serious Adverse Events

The investigator or designee must report all SAEs promptly to within 24 hours of first becoming aware of the event, and sending the SAE form to following methods:

Email:			
Email:			
Fax nu	mber:		

The written report should be submitted on the SAE form provided for this purpose. At the time of first notification, the investigator or designee should provide the following information, if available:

- Protocol number
- Reporter (study site and investigator)
- Subject's study number
- Subject's year of birth
- Subject's gender
- Date of first dose of IP(s)
- Date of last dose of IP(s), if applicable
- Adverse event term
- Date of occurrence of the event
- A brief description of the event, outcome to date, and any actions taken
- The seriousness criteria(on) that were met
- Concomitant medication at onset of the event
- Relevant medical history information
- Relevant laboratory test findings
- Investigator's opinion of the relationship to IP(s). ("Is there a reasonable possibility that the IP caused the SAE? Yes or No?")
- Within 24 hours of the initial notification, the investigator must provide a written SAE Report Form that describes the SAE to copy of the information to
- Any missing or additional relevant information concerning the SAE should be provided to the recipient(s) of the initial information as soon as possible on a follow-up SAE Report Form, together with the following information (AE, date of occurrence, subject ID, study ID, IP, and site number); this will allow the follow-up information to be linked to the initial SAE report. Ensure that any additional information requested about the event (e.g., hospital

reports, autopsy reports) is provided to the designated individual(s) as soon as it is available.

- Specific information may be requested by the Department using a follow-up request form.
- The investigator is required to comply with applicable regulations (including local laws and guidances) regarding the notification of his or her health authorities, IRB/ IEC, principal and coordinating investigators, study investigators, and institutions. The detailed reporting duties and division of responsibilities between the sponsor and will be provided in a separate document (see CNTX-4975i-OA-303 Safety Management Plan). Each investigator is obligated to learn about the reporting requirements for investigators in his or her country. The study monitor may be able to assist with this.

#### 11.2.7.2 Non-serious Adverse Events

Non-serious AEs will be recorded in the eCRF and reported by Therapeutics Corp.

### 11.3 Special Considerations

#### 11.3.1 Pregnancy

All women of childbearing potential who participate in the study should be counseled on the need to practice adequate birth control and on the importance of avoiding pregnancy during study participation. Women should be instructed to contact the investigator or study staff immediately if pregnancy occurs or is suspected.

Pregnancy testing will be conducted prior to administration of CNTX-4975-05 on every woman of childbearing potential. A woman who is found to be pregnant at the Screening Visit will be excluded from the study and considered to be a Screening failure.

A woman who becomes pregnant within 2 days of treatment with CNTX-4975-05 will be immediately discontinued from study participation. The investigator must report the pregnancy as if it were an SAE within 24 hours of learning of the pregnancy, to Pharmacovigilance using the Pregnancy Data Collection Form via the same fax number and/or email address as for SAE reporting. The investigator should contact the designated individual(s) who receive SAE notification and record information related to the pregnancy on an SAE and AE form (entering the event temporarily as non-serious on both forms) provided by the sponsor or its designee.

Early Termination Visit assessments are required as soon as possible after learning of the pregnancy. The investigator is also responsible for following the pregnancy until delivery or termination. These findings must be reported on the SAE and AE form and forwarded to the designated individual(s). The event meets the SAE criterion only if it results in a spontaneous abortion or a congenital anomaly.

#### 11.3.2 Overdose

The maximal dose of CNTX-4975-05 should not be exceeded during the study.

Overdose that occurs during the study will be treated and documented as an AE/UAE/SAE if it fulfills the criteria. If the overdose does not result in an AE, it should be reported in written form to the designated individual(s) who receive SAE notification. The information contained therein should include study site identification, reporter identification, subject identification, IP, dose, action taken, and any comments.

Page 69 of 89

Amendment 2 Version: 3.0

13-Jun-2019

13-Jun-2019

### 12 DATA SAFETY MONITORING BOARD

A Data Safety Monitoring Board will not be used in this study.

AD-MW-08.04 15-Apr-2016 Page 70 of 89

Amendment 2 Version: 3.0

#### 13 STATISTICS

The statistical analysis was developed to meet the requirements of the US FDA and the European Medicines Agency.

### 13.1 Study Endpoints

### 13.1.1 Primary Efficacy Endpoint

The primary endpoint is assessment of the CNTX-4975-05 treatment regimens, with the Breg Cooling Control Group as the standard, using a combination of 3 assessments of the index knee: 1) pain 30 minutes after CNTX-4975-05 injection (using the 0-4 scale of none, mild, moderate, moderately severe, and severe); 2) subject satisfaction with the treatment regimen; and 3) investigator satisfaction with the treatment regimen.

### 13.1.2 Secondary Efficacy Endpoints

Secondary efficacy endpoints include:

- Assessment of the primary combined outcome using the contralateral knee for the subjects who received bilateral injections and the index knee for all other subjects
- Assessment of the primary combined outcome for each subject type
- Assessment of the primary combined outcome, using the contralateral knee for the subjects who received bilateral injections
- Percent of Outcome Measures in Rheumatology-Osteoarthritis Research Society International (OMERACT-OARSI) responders at Week 8 for subjects with a single CNTX-4975-05 joint injection (index knee, moderate to severe pain index knee, pain not >3 for contralateral knee)
- Percent of OMERACT-OARSI responders at Week 8 for subjects with bilateral knee injections of CNTX-4975-05 (index knee, moderate to severe pain index knee, both knees meeting OMERACT-OARSI responder criteria)
- Percent of OMERACT-OARSI responders at Week 8 for subjects with a single CNTX-4975-05 joint injection (population with index knee, moderate to severe pain index knee, non-index knee with PJR/TJR)
- For each of the 3 types of subjects, the absolute change; the number of subjects who have ≥30%, ≥50%, ≥70%, or ≥90% improvement area under the curve; and landmark analysis on the 5 subscales of the KOOS through Week 8 using the average of both knees:
  - o Pain
  - Other symptoms
  - Activities of daily living
  - Sports and recreation
  - o QOL

- Assess the SS of treatment with CNTX-4975-05 IA injection for each of the 3 types of subjects, and all subjects in the trial
- For subjects with a PJR/TJR, assess their satisfaction with the CNTX-4975-05 IA injection versus their satisfaction with their knee with a PJR/TJR

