## 5.1.2 Clinical Experience

The efficacy and safety of CNTX-4975 in subjects with moderate-to-severe OA knee pain has been investigated in 7 studies. In an initial dose-ranging study in 16 subjects

(SAEs) was low, and none was thought to be related to the IP. Three of the studies reported no SAEs. In 1 study, an SAE was reported as possibly related (CNTX-4975-2-004-1, indication Morton's neuroma) and involved T-wave inversion. However, this event occurred in the placebo group and resolved without further treatment. Three other SAEs were listed as unrelated and involved chest pain (CNTX-4975-2-002-1, indication OA), femoral hernia (CNTX-4975-2-006-2; indication OA), and menorrhagia (CNTX-4975-2-005-2; indication lateral epicondylitis). One SAE was worsening of previous shoulder OA in study CNTX-4975-OA-502, noted as unrelated, with the subject continuing in the trial.

Most of the systemic adverse events (AEs) occurred with similar frequency in capsaicin-treated (all doses combined) compared to placebo-treated subjects. The exception from this was the frequency of initial pain from the injection. Intra-articular injection of capsaicin into the knee produced short-term pain, most often for a period less than 30 minutes. In the preliminary analysis of Study 114-02P, subjects typically indicated that the pain was tolerable (mean peak pain 5.4 on the 0-10 Numeric Pain Rating Scale [NPRS]). However, 4 of 40 subjects, asked to indicate whether the pain was tolerable, indicated that the pain was intolerable. In all instances, the

procedure pain was short-lived (typically under 1 hour) and was under satisfactory control at the time the patient was discharged from the clinic.

Study 4975-OA-501 included 30 subjects with OA of the knee whose index knee was treated with CNTX-4975 IA. The focus of this study was to further manage procedural pain. The results suggested the best approach included a combination of opioid pre-medication, 15 mL of lidocaine (2%, without epinephrine) IA 15-30 minutes before IP injection, combined with joint cooling.

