#### 9.5 Method of Assigning Subjects to Treatment Groups

All enrolled subjects will be assigned to CNTX-4975-05. Assignment to unilateral or bilateral injections will be determined by the subject's OA pain and previous joint replacement status. The subject's joint treatment regimen will be based on the site at which the subject is enrolled.

Unilateral or Bilateral Injections: The study population will contain 3 types of subjects, with a targeted minimum of 150 subjects of each type:

- 1. Subjects with unilateral or bilateral OA of the knee, with one knee (the index knee) with moderate to severe pain (K-L grade 1-4) and the other knee (the contralateral knee) with no to mild pain. These subjects will receive an IA injection in the index knee only.
- 2. Subjects with bilateral OA of the knees, with both knees having moderate to severe pain (K-L grade 1-4, with worse pain in the index knee). These subjects will receive an IA injection into each knee (1 week apart). The index knee in these subjects is the one with the worst pain with walking. Where both knees have equal pain with walking, then the knee on the subject's dominant side will be designated the index knee.
- 3. Subjects who have unilateral or bilateral OA of the knee, with one knee with moderate to severe pain (the index knee [K-L grades 1-4]) and previous PJR or TJR in the other knee (the contralateral knee). These subjects will receive an IA injection into the index knee only.

Joint Treatment Regimen: Each site will be randomly assigned 1 of the 5 joint treatment regimens to be employed for ALL subjects at that site. The joint treatment regimens are listed in Section 9.3.2.

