## **Anaphylactoid reaction**

These reactions produce the same clinical signs and symptoms anaphylactic reactions, but are not IgE mediated, but instead occur through a direct non-immune-mediated release of mediators from basophils and/or mast cells or can manifest from direct complement activation.

All subjects must be monitored for at least 30 minutes (or longer, as required by the protocol) after study drug injection to ensure that they do not have a hypersensitivity reaction/anaphylaxis. Vital signs (VS) are to be done pre-injection and 5 minutes after the injection, standing and sitting, and then vital signs must now be taken at 15 and 30 minutes (sitting only) after injection of study drug

Any subject that meets the criteria for anaphylaxis or anaphylactoid reactions, as described in the paper by Sampson et al. (2006) (see Appendix C) following the first/prior injection is prohibited from being re-treated with study drug.

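### The contralateral-knee composite, and on one reading the bilateral Week 8 responder rate, count only subjects who actually had both injections, and no rule covers a type 2 subject who misses the second

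*Combined protocol and SAP*

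**What the plan says.** Section 9.5 fixes the number of planned injections before treatment: "Assignment to unilateral or bilateral injections will be determined by the subject's OA pain and previous joint replacement status". Type 2 subjects, at least 150 of about 850, have moderate to severe pain in both knees and are planned for two injections a week apart.

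Section 13.1.2 (repeated in the synopsis) then defines the relevant secondary endpoints:

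- The first bullet is the primary combined outcome "using the contralateral knee for the subjects who received bilateral injections and the index knee for all other subjects".
- The third bullet selects on the same receipt of both injections but has no clause for anyone else.
- The bilateral responder bullet is "Percent of OMERACT-OARSI responders at Week 8 for subjects with bilateral knee injections of CNTX-4975-05", and it requires both knees to respond.
- One single-injection responder bullet is limited to "index knee, moderate to severe pain index knee, pain not >3 for contralateral knee". The other is limited to subjects with a replaced contralateral joint.

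The default efficacy set is ITT, meaning all enrolled subjects (Sections 13.3 and 13.4.3). Section 13.4 places the secondary endpoints in a fixed testing sequence. Section 13.4.1.1 tabulates withdrawals and reasons by subject type and injection procedure. No section says how to classify or score a type 2 subject who does not have the second injection.

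**The concern.** A type 2 subject may miss the second injection for several reasons. They may decline it, they may withdraw (Section 8.3), or they may be barred: under Section 11.2.1 a subject meeting the anaphylaxis criteria "following the first/prior injection is prohibited from being re-treated with study drug". Tolerance of the procedure is what the five regimens are compared on, so stopping after the first injection can itself be a result of the regimen. A set restricted to twice-injected subjects is then selected partly by the outcome under study.

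Two results are exposed. One is the third-bullet composite, which would lose the subjects who fared worst. The other is the bilateral responder rate if it is read as injections received. That rate serves the Section 6.2 objective of describing the benefit of treating bilateral OA, and a rate confined to those willing and able to continue answers a narrower question.

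**Working it through.** **Plan figures.** The plan gives no stopping rate, responder rate or SD, and about 850 subjects was chosen for safety exposure (Section 13.2). There is no calculation to reproduce. The first step below is a reading of the text; steps 2 and 3 are illustrations on assumed inputs.

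**Step 1. Where a type 2 subject with one injection falls.**

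| Endpoint | In or out |
|---|---|
| Primary composite (index knee) | In |
| Composite by subject type; KOOS by subject type | In |
| Mixed-knee composite (first bullet) | In, scored on the index knee |
| Contralateral composite (third bullet) | Out |
| Responders, contralateral pain not above 3 | Out, because both knees are moderate to severe |
| Responders, contralateral joint replacement | Out |
| Responders, bilateral injections | Out if the bullet means received; in if it means planned |

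ITT does not settle the last row, because the bullet itself defines the subset.

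**Step 2. Responder rate.** Let s be the share stopping after the first injection, p the both-knees rate in the twice-injected and q the rate in stoppers. The rate in those planned is (1 − s)p + sq. With p = 60% and q = 0:

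- s = 5%: 0.95 × 60 = 57%
- s = 10%: 0.90 × 60 = 54%
- s = 20%: 0.80 × 60 = 48%

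Of 150 type 2 subjects, 5-20% is 7.5 to 30 people.

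Between regimens, take p = 50% in both, with stopping of 5% v 20%. The received set shows 50% v 50%. The planned set shows 47.5% v 40.0%, a gap of 7.5 points. Over p = 40-60%, q = 0-20% and stopping pairs from 5% v 10% to 10% v 30%, the hidden gap is 1 to 15 points. The order can reverse: 50% v 55% received, with 5% v 25% stopping, becomes 0.95 × 50 = 47.5% v 0.75 × 55 = 41.3% planned.

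For scale, 150/5 = 30 type 2 subjects per regimen if spread evenly. Treating subjects as independent, power for 47.5% v 40% at 30 per arm is about 8%, and 80% power needs 686 per arm. The effect is therefore on the estimates more than on any test.

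**Step 3. Composite ratio, type 2 subjects only.** Assumed: a 0-100 score for each injection, normal and clipped to the range, SD 20, control mean 75. The ratio is test mean over control mean for the second knee.

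*Set A.* Test mean 52.5, correlation between injections 0.4-0.8, and every subject below a cut on the first score stops:

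| Cut | Stopping, control v test | All planned | Received both | Mixed (first bullet) |
|---|---|---|---|---|
| 35 | 2% v 19% | 0.71 | 0.74-0.77 | 0.67-0.70 |
| 45 | 7% v 35% | 0.71 | 0.76-0.81 | 0.66-0.69 |

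*Set B.* Test mean 51, correlation 0.3-0.8, stopping with probability 0.25-0.75 only after a first score below 50. All planned is 0.69, received both 0.70-0.77, mixed 0.65-0.69.

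*Set C.* Means as in B, correlation 0.6, stopping of 5% v 25% unrelated to the score. All three ratios are 0.69.

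Selection on tolerance can thus lift the received-only point estimate across the 0.7 used for the primary comparison. The mixed composite moves the other way because stoppers carry their poor index-knee score.

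**The case against.** A reader might infer that these subjects drop out of all three responder endpoints and that the bilateral endpoints as a group favour a regimen that deters a second injection. The documents do not support either as a general statement.

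- **Wording.** The responder bullet does not say received. The three responder bullets match the three subject types, and bilateral wording denotes the planned group elsewhere: in Schedule of Events footnote w (KOOS on both knees before the first injection) and in inclusion criterion 4. Read that way, stoppers stay in and would tend to count against the regimen. This stands. What remains is that the plan never says which reading applies or how a missed second injection is scored.
- **Direction.** The first-bullet composite keeps stoppers and leans against a deterring regimen, and stopping unrelated to tolerance causes no composite bias. This stands.
- **Poor experience is already counted.** The first injection enters the primary composite and the composite by subject type, and KOOS is also by type. This stands; the point touches secondary endpoints only.
- **Size.** The nearest figure, in Section 5.1.2, is that "4 of 40 subjects, asked to indicate whether the pain was tolerable, indicated that the pain was intolerable". It comes from a preliminary analysis of an earlier study under a different procedure, and it measures tolerability, not refusal of a second injection. Set A is a worst case in that everyone below the cut stops. At about 30 per regimen its received-only lower 95% limits would be roughly 0.62-0.70, so a false pass on 0.7 is unlikely.
- **Reporting.** Section 13.4.1.1 covers withdrawals with reasons. It does not cover subjects who skip the second injection and stay in the study.

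**Conclusion.** The point holds in a limited form. The third-bullet composite is explicitly conditioned on a post-treatment event although a baseline definition is available. The bilateral responder bullet can be read the same way, and on that reading a type 2 subject with one injection belongs to no responder set.

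The flattering direction applies to those two results only, and depends on poor tolerance driving stopping (for responders, on stoppers being less likely to meet the both-knees criterion). The mixed composite leans the other way.

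The size cannot be fixed from the documents. On assumed stopping of 5-20%, a 60% responder rate overstates the planned-set rate by 3 to 12 points, and the type 2 composite ratio could be overstated by about 0.01 to 0.10 in the scenarios tried. It is worth correcting because the text is unresolved, the objective is about treating bilateral OA, and the remedy is cheap.

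**What to change.** In Section 13.1.2 and the synopsis:

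1. Define the bilateral responder set as all subjects enrolled as type 2 who received the first injection, and count a missed second injection as not meeting the both-knees criterion.
2. Report, by regimen and beside the contralateral composite, how many type 2 subjects had no second injection and why, including those who stay in the study. State that this composite describes only twice-injected subjects, since no post-injection score for the second knee exists without the injection.
3. Optionally, add a sensitivity analysis giving the lowest score to those who stopped for procedure pain or dissatisfaction. It should not be the main version: giving every stopper in Set A a score of 0 yields ratios of 0.53-0.64 against 0.71, so it overshoots.

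The cost is a wording change, one reason field for a missed Visit 4 and a somewhat less favourable bilateral responder rate. No visits are added, and no treatment rule changes.

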### 13.1.3 Exploratory Efficacy Endpoints

Exploratory efficacy endpoints include:

- Likelihood of the need for joint replacement surgery, based on KOOS subscales and SS outcomes, from Baseline through Week 8
- SS with the treatment of the index knee through Week 8 of the trial (7-point Likert Scale where 1=completely dissatisfied and 7=completely satisfied)
- The effect of subject characteristics (including K-L grade, sex, BMI, age, unilateral/bilateral knee OA, bilateral knee OA treatment, and history of contralateral PJR/TJR) on the analgesic efficacy of CNTX-4975-05, using the KOOS subscales at each study visit through Week 8
- Frequency of use of background analgesic medication for pain in the injected knee(s) throughout the study period.
- Assessment of the mean of the individual outcome measures, using the average of both knees for the subjects who received bilateral knee injections

## 13.1.4 Safety Endpoints

Safety endpoints include:

- AEs
- Vital signs
- Clinical laboratory evaluations (hematology, chemistry, and urinalysis)
- 12-lead ECGs
- Physical examination (including the presence or absence of an effusion in the index knee, periarticular pain/tenderness)
- Concomitant medications and therapies
- Degree of procedure pain (not recorded as AEs)
- Local physical findings after injection of the index knee
- Injection site assessment of erythema and edema
- Sensory testing

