- n. The injection site will be examined and assessed for erythema and edema by site personnel (using a categorical 4-point scale of none, mild, moderate, or severe [0-3]) on Study Day 1 (Treatment) before injection, after the injection at 1 and 2 hours post-dose, and at the Week 4 Visit. For bilateral knee injections, injection site examinations will be performed before and after each injection. Significant bruising or other clinically significant injection site reactions will be recorded as AEs.
- o. Procedure pain will be assessed by asking subjects to rate their index knee pain (1) at rest prior to pre-medication; (2) prior to IA lidocaine (without epinephrine); (3) at rest 10 minutes (± 2 minutes) after IA lidocaine (without epinephrine); (4) at 30 minutes (± 5 minutes) after IA injection of CNTX-4975-05; and (5) at rest at the 1-hour and 2-hour time points after IA injection of CNTX-4975-05 (± 10 minutes).
- p. Immediately prior to leaving the clinic, the subject will be asked how satisfied they were with the treatment procedure at that visit, using a 7-point Likert Scale where 1=completely dissatisfied and 7=completely satisfied. Subjects with a PJR/TJR will also compare their satisfaction with PJR/TJR versus the CNTX-4975-05 treatment.
- q. Subjects will be asked whether they would undergo the study treatment again.
- r. The investigator will rate their satisfaction with each subject's study treatment (at V2 and V4 if applicable) and the treatment procedure (at V7).
- s. The investigator will judge the likelihood of the need for joint replacement surgery, based on KOOS subscales and subject satisfaction outcomes. The subject will judge the likelihood of the desire for joint replacement surgery, based on their personal response to treatment with CNTX-4975-05.
- t. Collection of AEs will begin from the time of signing the informed consent form through the Week 8/ET Visit. On Day 1, the AE assessment must be performed pre-dose. Treatment-emergent AEs will be collected from the time of the injection of CNTX-4975-05 through the Week 8/ET Visit. Potentially

13-Jun-2019 Amendment 2 Version: 3.0

AD-MW-08.04 15-Apr-2016 Page 17 of 89

- related AEs that are ongoing at the Week 8/ET Visit will be followed until they are stable, resolved, no longer clinically significant (in the opinion of the investigator), or until 4 weeks after the study is completed.

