#### 11 ADVERSE EVENTS

#### 11.1 Definitions

#### 11.1.1 Adverse Events

An AE is defined as any untoward medical occurrence in a patient or clinical investigation subject administered a pharmaceutical product that does not necessarily have a causal relationship with the product. An AE can therefore be any unfavorable and unintended sign (including a new, clinically important abnormal laboratory finding), symptom, or disease, temporally associated with the product, whether or not related to the product.

Pre-existing diseases or conditions will not be considered AEs unless there is an increase in the frequency or severity, or a change in the quality of the disease or condition (worsening of a pre-existing condition is considered an AE).

Events occurring in subjects treated with placebo or active comparator or during treatment-free periods of the study are also considered AEs.

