#### 11.1.3 Serious Adverse Events

An SAE is any untoward medical occurrence that at any dose

- results in death
- is life-threatening NOTE: The term "life-threatening" in the definition of "serious" refers to an event in which the patient was at risk of death at the time of the event; it does not refer to an event

which hypothetically might have caused death if it were more severe.

• requires inpatient hospitalization or prolongation of existing hospitalization NOTE: Inpatient hospitalization is defined as 24 hours in a hospital or an overnight stay. An elective hospital admission to treat a condition present before exposure to the test drug, or a hospital admission for a diagnostic evaluation of an AE, does not qualify the condition

or event as an SAE. Further, an overnight stay in the hospital that is only due to transportation, organization, or accommodation problems and without medical background does not need to be considered an SAE.

- results in persistent or significant disability/incapacity
- is a congenital anomaly

NOTE: A congenital anomaly in an infant born to a mother who was exposed to the IP during pregnancy is an SAE. However, a newly diagnosed pregnancy in a subject that has received an IP is not considered an SAE unless it is suspected that the IP(s) interacted with a contraceptive method and led to the pregnancy.

• is an important medical event

NOTE: Medical and scientific judgment should be exercised in deciding whether it is appropriate to consider other situations serious, such as important medical events that may not be immediately life-threatening or result in death or hospitalization but may jeopardize the patient or may require intervention to prevent one of the other outcomes listed in the definition above.

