### 11.1.4 Significant Adverse Events

Other significant AEs are defined as marked hematological and other laboratory abnormalities (other than those meeting the definition of serious) and any events that led to an intervention, including withdrawal of IP, dose reduction, or significant additional concomitant therapy.

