#### 11.2 Management of Adverse Events

Adverse events will be collected from the time of signing the ICF through the Week 8/ET Visit.

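### The blanket rule that procedure pain is not recorded as an AE conflicts with the protocol's own AE, SAE and significant-AE definitions and needs a stated limit

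*Combined protocol and SAP*

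**What the plan says.** Section 13.1.4 of the protocol lists among the safety endpoints "Degree of procedure pain (not recorded as AEs". The Synopsis carries the same entry. Neither place limits it by severity, duration, treatment needed or seriousness.

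The definitions in section 11 contain no matching exclusion:

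- 11.1.1: "An AE is defined as any untoward medical occurrence in a patient or clinical investigation subject administered a pharmaceutical product", whether or not it is caused by the product.
- 11.1.3: "An SAE is any untoward medical occurrence that at any dose" meets one of the listed criteria, hospitalization among them.
- 11.1.4: significant AEs include "any events that led to an intervention, including withdrawal of IP, dose reduction, or significant additional concomitant therapy".

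Footnote t of the Schedule of Events (Table 2-1) says "On Day 1, the AE assessment must be performed pre-dose". Its next sentence reads "Treatment-emergent AEs will be collected from the time of the injection of CNTX-4975-05 through the Week 8/ET Visit".

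Procedure pain has its own data stream. Section 10.3.3.3 has it rated in five categories before and after the lidocaine, and at 30 minutes, 1 hour and 2 hours after the study drug. The Day 3 calls repeat the rating. Section 13.4.4.8 tabulates the categories at each time point.

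**The concern.** It is reasonable not to transcribe every routine pain rating as an AE in a study of an injection that is expected to hurt. The difficulty is that the rule is written without a limit, so it also covers pain that leads to admission, needs substantial unplanned treatment, or stops a subject from having the second knee injected.

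A 0-4 rating does not replace an AE record for such an event. The rating gives intensity at fixed times. An AE record under section 11.2.4 also gives seriousness, action taken, outcome and relationship to the product.

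The point matters more here than in most studies. Section 5.1.2 names initial injection pain as the exception to otherwise similar systemic AE frequencies against placebo, and control of that pain is what the five regimens vary. Section 13.4.4.1 displays AEs by injection procedure. Section 9.5 assigns one regimen to each whole site, so if sites read the rule differently, the difference in coding is confounded with regimen.

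**Working it through.** The plan gives no figure to reproduce on this point. The check is a comparison of sections, followed by four cases.

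**Step 1. How an event becomes an SAE.** Section 11.1.3 starts from any untoward occurrence. Section 11.2.3.1, however, describes an SAE as an AE that satisfies the seriousness criteria, and 11.2.3.2 asks the investigator to judge whether the AE does so. On that route an event must first be an AE. A site told that procedure pain is not an AE has a textual reason never to make the seriousness judgement.

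**Step 2. Is there an escalation rule elsewhere?** There is one for neighbouring findings. Section 10.3.3.2.4 and footnote n turn clinically significant injection site reactions into AEs (10.3.3.2.4 excepts erythema and edema). Neither says whether pain counts as such a reaction. Section 10.3.3.3, which governs the pain ratings, has no escalation rule.

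**Step 3. Four cases.**

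| Event | Under 13.1.4 read literally | Under 11.1.1, 11.1.3 and 11.1.4 | Where it would still be visible |
|---|---|---|---|
| Severe at 30 minutes, then settles | Not an AE | Untoward occurrence, 11.1.1 | Pain table; primary composite |
| Leads to a qualifying hospital stay | Not an AE, so perhaps never tested for seriousness | SAE, 11.1.3 | Pain ratings only at their fixed times |
| Needs significant additional therapy | Not an AE | Significant AE, 11.1.4 | Concomitant medication data |
| Second injection in a bilateral subject not given | Not an AE | Significant AE, if this counts as withdrawal of the product | Injection records; disposition table if the subject withdraws |

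The first case loses little. In the other three the two sets of rules give different answers, and the event could be missing from the AE, SAE or AE-discontinuation tables of section 13.4.4.1. The fourth bears directly on the discontinuation table: each knee receives one injection, so apart from an interrupted injection the second knee is the main place where treatment can be discontinued.

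**Step 4. Day 1 timing.** Footnote t fixes a pre-dose AE check on Day 1 and sets no clock time for one after dosing. The collection window is nevertheless continuous: section 11.2 states "Adverse events will be collected from the time of signing the ICF through the Week 8/ET Visit", footnote t collects treatment-emergent AEs from injection, and section 11.2.2 requires open questions at each visit and counts clinically relevant findings there as AEs. The wording is unclear, but it leaves no gap in collection.

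**Step 5. Background rate.** Section 5.1.2 reports that 4 of 40 subjects, "asked to indicate whether the pain was tolerable, indicated that the pain was intolerable". The proportion is 4/40 = 0.10. The exact (Clopper-Pearson) 95% limits are:

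- lower: 2.5% quantile of Beta(4, 40 − 4 + 1) = Beta(4, 37) = 0.0279
- upper: 97.5% quantile of Beta(4 + 1, 40 − 4) = Beta(5, 36) = 0.2366

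So the rate is 10% (2.8% to 23.7%). This shows that pain which subjects find intolerable has occurred with this route of administration. It does not estimate how often such pain would meet an AE or SAE criterion here.

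**The case against.** The strongest reply is that the parenthesis is a label in an endpoint list, attached to the 0-4 rating and absent from the operative AE section. Read naturally, it says only that routine ratings are not copied onto AE forms. Section 11.1.3 has no exclusion, and 11.2.7.1 requires all SAEs to be reported within 24 hours. Section 11.1.4 classifies AEs, so it does not by itself make something an AE. That reading is plausible and probably the intended one, but the text does not say it, and 11.2.3.1 and 11.2.3.2 make the literal reading workable for a site. The case for a clarification stands.

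Several stronger conclusions that a reader might infer are not supported:

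- **That procedure pain is exempt from SAE reporting.** No text says so. The sections conflict; they do not state an exemption.
- **That the post-injection period on Day 1 has no AE collection.** The second sentence of footnote t and sections 11.2 and 11.2.2 cover it.
- **That the regimen comparison omits this harm.** Pain at 30 minutes is one of three equally weighted components of the primary comparison (13.4.3.1), and all ratings are tabulated (13.4.4.8). Reapplied cooling, concomitant medication and withdrawals by injection procedure are also recorded.
- **That the 10% rate can be projected onto the 850 planned subjects.** It comes from a preliminary analysis of one earlier study. Section 5.1.2 adds that the pain was short-lived and under control by discharge. The procedures here differ in several ways, so even the direction of any difference is unknown.
- **That procedure pain is the main known harm.** It is a known harm. The adverse event of special interest is severe allergic reaction.

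**Conclusion.** The concern holds as an unreconciled conflict within the protocol. An unlimited rule in 13.1.4 and the Synopsis contradicts the definitions in 11.1.1 and 11.1.3 and sits badly with 11.1.4. Followed literally, it could keep serious or treatment-requiring procedure pain out of the AE and SAE tables shown by injection procedure. Pain intensity would still be reported.

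The number of affected events cannot be computed from the documents. It is likely to be a small subset of subjects with procedure pain, but that subset is the one a safety reviewer would most want to see. The conclusion assumes that at least some sites would take the parenthesis at face value and that the eCRF guidelines, which are not in the documents, do not already correct it. The change is worth making because it is cheap and uses criteria the protocol already contains.

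**What to change.** Keep the 0-4 ratings and their tabulation. In the Synopsis and section 13.1.4, replace the parenthesis with wording to this effect:

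*Routine procedure-pain ratings are not in themselves AEs. Procedure pain is also recorded as an AE, and reported as an SAE where applicable, when it meets a seriousness criterion in 11.1.3 or a criterion in 11.1.4, that is, significant additional concomitant therapy or withdrawal of the product, including the second injection not being given because of the pain.*

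Put the same sentence in section 10.3.3.3, where site staff will look for it. No new severity threshold is needed, since the documents give no basis for one.

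As a clarification, footnote t should say that the pre-dose AE check on Day 1 is in addition to AE enquiry after dosing on each injection day.

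The cost is protocol and eCRF-guideline wording and a short note to sites. The downside is slightly higher AE counts. If subjects have been treated before the change takes effect, the report should state from when the rule applied, because AE counts before and after will not be fully comparable.
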